## 9.2 Sample Size and Randomization

Our pilot study demonstrates an increase in HF HRV after 6-week exhale=inhale slowing breathing (N=9, mean  $58 \pm SD 248$ ) or after 6-week exhale>inhale slow breathing (N=9,  $173 \pm 531$ ). The pooled SD from the two groups is 406, which is similar to published values among health adults. By 12 weeks, we expect that the difference in HF HRV between the two groups will be 265, and a sample size of 38 per arm will give us 80% power to detect this effect at a 0.05 two-sided significance level. Accounting

for 20% drop out, we will enroll 50 participants per arm. If the difference detected is 280 and 300, the power will be 84% and 89%, respectively.

With 50 participants per arm, we will have 80% power to detect a 5.2-point difference in 12-week PROMIS Anxiety Scale reduction assuming a SD of 8 and a type I error of 0.05. With a total N of 76, the study is able to detect a correlation coefficient of 0.7 between changes in HF HRV and changes in PROMIS Anxiety with a margin of error of 0.14.

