### 9.6 Data Analyses

Standard graphing and screening techniques will be used to detect outliers and to ensure data accuracy. Distributions of continuous outcomes will be assessed for normality. If normality is violated, proper data transformation will be applied or non-parametric analysis methods will be considered. Summary statistics for both continuous and categorical variables will be provided by randomization groups to describe the study sample.

This is a two-arm randomized study with repeated measures. The effects of either of the slow breathing interventions on HF HRV, PROMIS Anxiety and other endpoints will be estimated as within-subject mean change from baseline to 12 week, along with their 95% confidence intervals. A paired t-test will be performed to compare the endpoints within the group. The difference between the two treatment groups will be estimated by the mean difference in the within-subject changes, along with their 95% confidence intervals, and a t-test will be performed. If normality is violated, proper data transformation will be applied.

Mixed-effect models will also be used to analyze the data with a random subject effect and with intervention (exhale>inhale vs. exhale=inhale), time points (6 week and 12 week), baseline measurements and interaction between intervention and time points as fixed effects. Change in the outcomes from baseline to 6/12 weeks will be used as responses. We will include covariates age, gender, and baseline psychological stress in the models to adjust for their effects.

Specific inferences on effects of interest will be made by reporting a point estimate along with a 95% confidence interval and the p-value. Hypotheses will be tested at the level of  $\alpha=0.05$ .

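### Section 9.2 mislabels two planning figures: 406 is not the pooled within-group SD (414), and the 5.2-point PROMIS difference belongs to 38 evaluable per arm, not 50

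*Combined protocol and SAP*

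**What the plan says.** Section 9.2 reports pilot changes in HF HRV over 6 weeks: mean 58 (SD 248) with exhale=inhale and mean 173 (SD 531) with exhale>inhale, 9 participants in each arm. It then states: "The pooled SD from the two groups is 406". For an expected 12-week difference of 265, two-sided 0.05, it says "a sample size of 38 per arm will give us 80% power to detect this effect", and it gives powers of 84% and 89% for differences of 280 and 300. Allowing "for 20% drop out, we will enroll 50 participants per arm".

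For the other outcome that section 3 calls primary, the text is: "With 50 participants per arm, we will have 80% power to detect a 5.2-point difference in 12-week PROMIS Anxiety Scale reduction", with SD 8 and type I error 0.05. For Aim 3 it says "With a total N of 76, the study is able to detect a correlation coefficient of 0.7", "with a margin of error of 0.14".

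Section 9.6 gives the between-group analysis: "The difference between the two treatment groups will be estimated by the mean difference in the within-subject changes", with a t-test. Mixed models on change are planned as well.

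**The concern.** Two figures do not follow from the inputs printed beside them.

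- **SD.** With equal arms, the pooled SD is the root mean square of the two arm SDs. SDs as far apart as 248 and 531 give a value above 406. A two-sample t-test on change scores uses this within-group SD, and the 38 per arm and the three HF HRV powers all rest on the figure chosen.
- **PROMIS sample size.** The HF HRV and correlation calculations use evaluable numbers (38 per arm; 76 in total). The PROMIS sentence between them names 50 per arm, which is the enrolled number, and mentions no dropout.

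These sentences are the power justification for the two primary outcomes. A reader who re-derives them gets different answers and cannot tell which numbers are enrolled and which are analysed. If the SD error were large, the trial could be too small for HF HRV, so the size of the error has to be checked.

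**Working it through.** All inputs are in section 9.2. The tests are two-sided at 0.05. Sidedness is not restated for PROMIS, so two-sided is assumed as for HF HRV. Power is from the two-sample t-test (noncentral t).

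**1. Reproduce the plan's HF HRV figures with its own SD.** With SD 406 and difference 265, 80% power needs 37.8, so 38 per arm. At 38 per arm the powers for 265/280/300 are 80.2/84.3/88.9%, which match the stated 80/84/89%. The stated powers reproduce for SDs of about 405 to 408, so 406 is the SD that was used.

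**2. Check the SD.**

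- Within-group sum of squares: 8 × 248² + 8 × 531² = 8 × (61,504 + 281,961) = 2,747,720.
- Pooled within-group SD: √(2,747,720 / 16) = **414.4**. Rounding of the printed SDs allows only 413.9 to 414.9.
- SD of all 18 changes ignoring arm: the overall mean is 115.5 and each arm mean lies 57.5 from it, so the between-arm sum of squares is 18 × 57.5² = 59,512.5. The SD is √((2,747,720 + 59,512.5) / 17) = **406.4**.

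So 406 comes from the same pilot data, but it is the SD of the combined sample.

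**3. HF HRV power with SD 414.4.**

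| Difference | Stated | 38 per arm | 40 per arm |
|---|---|---|---|
| 265 | 80% | 78.6% | 80.6% |
| 280 | 84% | 82.8% | 84.7% |
| 300 | 89% | 87.6% | 89.2% |

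The normal approximation at 38 per arm gives 79.6/83.8/88.4%. For 265, 80% power needs 39.4, so 40 per arm (38.4, so 39, by normal approximation).

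**4. Enrolled and evaluable numbers.** 50 × 0.80 = 40. Reaching 38 from 50 means a loss of 12/50 = 24%, not the stated 20%. In the other direction, 38/0.80 = 47.5, so enrolling 50 already had some slack.

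**5. PROMIS Anxiety, SD 8.**

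| Analysed per arm | Difference at 80% power | Power for 5.2 points |
|---|---|---|
| 38 | 5.21 | 79.9% |
| 40 | 5.07 | 81.9% |
| 50 | 4.53 | 89.6% |

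Other readings at 50 per arm do not give 5.2 at 80% power: one-sided 0.05 gives 4.01 and alpha 0.025 gives 5.00. An SD of about 9.2 would be needed.

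**6. Correlation.** 76 = 2 × 38. With Fisher's z, r = 0.7 and N = 76, the 95% interval is 0.563 to 0.799. The lower margin is 0.700 − 0.563 = 0.137, which agrees with the stated 0.14. At N = 80 the interval is 0.568 to 0.797, with a lower margin of 0.132. The correlation figure is therefore correct. It also supports 38 per arm as the basis of the PROMIS figure.

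**The case against.** The best defence is that nothing in the trial turns on this. The gap between 406 and 414 is 2% in a planning value. Under normality, a pilot SD of 414 on 16 degrees of freedom has a 95% interval of about 309 to 631, so 8 units are negligible beside the real uncertainty. The plan also says 406 resembles published values, which cannot be checked here. Mixed models adjusted for baseline are planned too, and their residual SD is neither figure. On PROMIS, reading 50 as enrolled and 38 as evaluable makes 5.2 right and leaves only a missing word. The error, read literally, is in the cautious direction. Finally, planning on 38 when 40 are expected is legitimate, and the correlation calculation contains no error.

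Most of this stands as to weight. It does not remove the faults. The text presents 406 as computed from the two pilot groups, and pooled SD in a two-sample calculation means the within-group figure. The PROMIS sentence fails if 50 are analysed (4.5 points), and it also fails if 50 are enrolled with the stated 20% dropout (40 per arm, 5.1 points). It holds only for 38, a number that the sentence does not give. Nor is 40 per arm only a matter of taste: once the SD is 414, 38 no longer gives the stated 80% by t-test, and 40 does.

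**Conclusion.** Both figures are wrong as labelled, and the consequence is small. The pooled within-group SD is 414, not 406; at 38 per arm this lowers t-test power by about 1.5 points, to 78.6% for a difference of 265. The 5.2-point PROMIS difference is the 80%-power figure for 38 analysed per arm. Enrolment of 50 per arm needs no change, because the 40 left after 20% dropout meet all three stated HF HRV powers with the correct SD.

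This rests on the pilot SDs and arm sizes as printed, two-sided 0.05 for both outcomes, and the unadjusted t-test of section 9.6. It does not say that 414 is a better forecast of the trial's SD than 406, only that 414 is what the label describes and what that test uses.

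**What to change.** In section 9.2:

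- Give the pooled within-group SD as 414.
- Use 40 evaluable per arm (50 enrolled less 20%) in all three calculations: HF HRV power of 81/85/89% for differences of 265/280/300; 80% power for a 5.1-point PROMIS Anxiety difference with SD 8; and, for a correlation of 0.7 with total N = 80, a margin of about 0.13.
- Label each sample size as enrolled or evaluable, and state that the PROMIS calculation is two-sided if that is intended.

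The change to the correlation sentence is for consistency only. If the team prefers to keep 38 per arm as a cautious figure, the PROMIS sentence should say 38 evaluable, and the HF HRV powers at SD 414 should read 79/83/88%.

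The cost is wording in one section. Enrolment (100 in total), tests and outcomes stay as they are, and at 40 evaluable per arm every restated figure is at least as favourable as the one now printed.

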## 9.3 Definition of Populations

All analyses will be performed as intention-to-treat. Our intent-to-treat population will include all participants who are randomized with baseline assessment and at least one post-randomization assessment.

## 9.4 Interim Analyses and Stopping Rules

We will not conduct interim analyses of 6 and 12-week outcomes in this clinical trial. After reaching 100% enrollment, baseline data will be analyzed to submit reports to NCCIH and prepare for second phase of grant award (R33). We will monitor subject accrual, adherence to interventions, and safety during the study period. [name] will present data on subject accrual with research staff and IMC. The enrollment period will be 15 months with an anticipated enrollment rate of 7 participants per month.

SAE's related to the intervention will suspend enrollment and/or the study intervention until a safety review is convened (either routine or ad hoc) by IMC to determine whether the study intervention should continue per protocol, proceed with caution, be further investigated, discontinued, or be modified and then proceed. If non-serious adverse events are related to breathing practice, then the breathing protocol will be modified to avoid adverse events. If the frequency of non-serious adverse events is higher than anticipated or alters the benefit risk ratio as determined by the IMC and the principal investigator, the study investigators will also modify the breathing protocol. Two or more specific adverse events among subjects will prompt modification of the breathing protocol.

## 9.5 Outcomes

### 9.5.1 Primary Outcome (Study Aim 1)

Assessment will occur at the Vanderbilt Autonomic Dysfunction Center as per standardized protocol. Blood will be analyzed in the Vanderbilt University Medical Center laboratory according to standard procedures. Assessments will be performed at baseline, 6, and 12 weeks.

**Physiological stress:** We will estimate autonomic tone of participants by standard autonomic testing of cardiovagal and sympathoneural functioning including heart rate variability and baroreflex sensitivity. Subjects will have fasted the night before testing, and testing will occur at the same time of the day for each subject to account for temporal variations of autonomic tone.

**(1) Heart rate variability:** Heart rate variability determines the cardiac autonomic tone of the subject, measuring instantaneous heart rate fluctuations in beat-to-beat intervals during continuous electrocardiographic monitoring with power spectral analysis. Spectral analysis detects beat-to-beat values of R-R intervals and blood pressure values will be interpolated, low pass filtered (cutoff 2 Hz) and resampled at 4 Hz. Data segments of at least 300 seconds during 10 minutes of undisturbed recordings, will be used for spectral analysis.

Subjects will be asked to maintain a regular breathing frequency paced to an auditory signal at 12 cycles per minute during recordings to control for confounding of respiratory sinus arrhythmia from respiration frequency. Linear trend will be removed and power spectral density will be estimated with the fast Fourier transform-based Welch algorithm using segments of 256 data points with 50% overlapping and Hanning window. The power in the frequency range of low frequencies (LF: 0.04 to <0.15 Hz), and high frequencies (HF: 0.15 to <0.40 Hz) will be calculated according to the Task Force recommendations. We will use the HF component of heart rate variability as an assessment of vagal control to the heart, and the LF component of the systolic blood pressure oscillation as an

indicator of sympathetic modulation.

**(2) Baroreflex sensitivity:** Baroreflex sensitivity will be measured through changes in heart rate and blood pressure while deep breathing (6 breaths per minute) for one minute, Valsalva maneuver, and 10 minute standing. Testing will occur in a relaxing environment, with adequate time for heart rate response to normalize tests. Heart rate will be monitored with a 3-lead electrocardiogram (EKG) and continuous non-invasive finger blood pressure measurements. Baroreflex sensitivity will be determined based on these measurements through spectral analysis using a transfer function analysis.

For heart rate response to deep breathing (E:I ratio), the patient will be asked to breathe deeply and slowly (about six breaths per minute) for at least one minute while heart rate is recorded. The ratio of maximum to minimum R-R interval will be calculated and compared to normative data.

- For the Valsalva maneuver, subjects will be asked to breathe into a closed tube, generating at least 40 mm Hg of pressure for at least 10 seconds. Heart rate and beat-to-beat blood pressure variability (BPV) will be measured. A Valsalva ratio will be calculated and compared to normative data for gender and age. The blood pressure response will be inspected for any evidence of sympathetic dysfunction (for example, significant blood pressure dip during phase II of Valsalva, or failure for blood pressure to increase during phase IV).

- For standing tests, subjects will be placed on an examination table, and then asked to stand-up for 10 minutes. BP and EKG recording will occur throughout the tilt.

**(3) Catecholamines:** Plasma norepinephrine and epinephrine levels will be measured at baseline, 6 and 12 weeks in supine and standing positions. Catecholamine samples will be drawn after 20 minutes of rest with an intravenous catheter in place. After centrifugation, plasma will be separated and stored at -70 °C until analyzed. Catecholamines analyses will be performed using high-performance liquid chromatography with electrochemical detection.

### 9.5.2 Secondary Outcomes (Specific Aims 2 and 3)

#### Specific Aim 2

**Psychological stress:** Psychological effects related to relaxation will also be assessed at baseline, 6, and 12 weeks. Questionnaires will be administered online through the RedCap data capture system. Participants unable to access the questionnaires online will be given printed copies at scheduled research visits.

#### **(1) Anxiety:**

- Anxiety will be measured with the PROMIS Anxiety computerized adaptive test (CAT)

(<http://www.nihpromis.org/measures/domainframework1>). This 29 item instrument assesses symptoms of self-reported fear, anxious misery, hyperarousal, and somatic symptoms related to arousal. The CAT allows for participant responses to guide the system's choice of subsequent items from the full item bank. PROMIS Anxiety correlates with PANAS Negative Affect which we used in our pilot study. PROsetta Stone® provides a conversion of PANAS scores to PROMIS Anxiety (<http://www.prosettastone.org>). We used this conversion table to estimate the baseline and change in PROMIS Anxiety used in our statistical plan below. PROMIS Anxiety has been validated among health adults.

We will administer other instruments of anxiety and stress as secondary measurements.

This will provide validation of results and inform translation to other clinical populations in the future

- Anxiety Sensitivity Index-3 (ASI-3) This 18-item instrument measures an individuals beliefs about feared consequences of symptoms associated with anxious arousal. This instrument measures three components: physical, social, and cognitive concerns.
- Beck Anxiety Inventory: This 21 item instrument measures anxiety in adults and has been shown to be valid and reliable.
- Body Vigilance Scale: This is a validated scale to measure conscious attendance to internal cues and is validated in healthy and anxiety disorder adults.
- Panic Disorder Severity Scale: This is a 7 item scale that measures panic disorder and agoraphobia symptom severity among adults that has shown to be valid and reliable.
- Perceived Stress Scale-10 (PSS): This 10 item instrument measures an individuals perceived stress.

**(2) Affect:** Negative affect will be measured with the PROMIS Depression CAT and PANAS-X. This 28 item instrument assesses negative mood, negative views of the self, negative social cognition, and decreased positive affect and engagement. PROMIS Depression has been validated among healthy adults and chronic disease populations. The PANAS-X will be used to assess affect over the past week. This is a 60 item instrument that has been shown to be valid and reliable among healthy adults.

**(3) Arousal:** Relaxation is associated with decreased arousal and increased sleepiness. To account for changes in arousal we will measure daytime sleepiness with the Epworth Sleepiness Scale. We will also administer the PROMIS Sleep Disturbance instrument to assess sleep quality.

**Fidelity measures:** We will assess fidelity to breathing interventions through direction observation of the mind-body teacher, self-report, and biometric garments-HEXOSKIN.

(1) **Self-report:** Each week, mind-body teachers observe participants performing the practice along with an audible metronome to measure breath rate and length of exhale and inhale. Mind-body teachers evaluate participate engagement, quality of technique, and breathe rate and exhale/inhale length (See Appendix for mind-body fidelity tracking form). Also each week, participants are asked how frequently they practiced at home by the mind-body teacher.

(2) **Remote biometric garment:** Lastly, we will use biometric garments, HEXOSKIN, to ascertain remote adherence to home breathing practice. As described previously, HEXOSKIN accurately records respiratory parameters including breathing rate, length of exhale/inhale through thoracic and abdominal strain gauges embedded in the shirt. Data for is stored in a small unit worn in the shirt. Each participant will be asked to wear a HEXOSKIN shirt during practice for one week for two time periods between weeks 3 to 8 and weeks 9 to 12. For 2-3 nights during each of these weeks the participant will be asked to keep the shirt on overnight to monitor sleep. Participants will return the shirt after one week, and data from the device will be downloaded for analyses. We will use VivoSense software with the Complex Respiratory Module to analyze breathing intervention fidelity (Vivonoetics, San Diego, CA).

## Specific Aim 3

We will compute the correlation between physiological and psychological changes (e.g. changes in heart rate variability correlated with changes in perceived stress).

### 9.6 Data Analyses

Standard graphing and screening techniques will be used to detect outliers and to ensure data accuracy. Distributions of continuous outcomes will be assessed for normality. If normality is violated, proper data transformation will be applied or non-parametric analysis methods will be considered. Summary statistics for both continuous and categorical variables will be provided by randomization groups to describe the study sample.

This is a two-arm randomized study with repeated measures. The effects of either of the slow breathing interventions on HF HRV, PROMIS Anxiety and other endpoints will be estimated as within-subject mean change from baseline to 12 week, along with their 95% confidence intervals. A paired t-test will be performed to compare the endpoints within the group. The difference between the two treatment groups will be estimated by the mean difference in the within-subject changes, along with their 95% confidence intervals, and a t-test will be performed. If normality is violated, proper data transformation will be applied.

Mixed-effect models will also be used to analyze the data with a random subject effect and with intervention (exhale>inhale vs. exhale=inhale), time points (6 week and 12 week), baseline measurements and interaction between intervention and time points as fixed effects. Change in the outcomes from baseline to 6/12 weeks will be used as responses. We will include covariates age, gender, and baseline psychological stress in the models to adjust for their effects.

Specific inferences on effects of interest will be made by reporting a point estimate along with a 95% confidence interval and the p-value. Hypotheses will be tested at the level of  $\alpha=0.05$ .

Based on our pilot study, we anticipate 20% missingness on post-randomization assessment. Mixed-effects models are robust in the sense that they can include subjects with missing data at one time point (6 week or 12 week) to estimate the effects of interest. We will also perform multiple imputation for missing data to corroborate our findings. Specifically, all the baseline variables and outcome variables will be included in the imputation model, and flexible additive imputation models and predictive mean matching approach will be used to impute missing values. We will use Rubin's method to combine the estimated regression coefficients and variances from the models based on ten imputed complete data sets. A Pearson correlation coefficient between changes in HF HRV and changes in PROMIS Anxiety will be calculated at each post-randomization assessment, for each intervention group or for all the participants respectively, along with 95% confidence interval. In addition, linear regression analysis of HF HRV changes on PROMIS Anxiety changes, age and gender will be conducted.

Per-protocol analysis will be also performed as a sensitivity analysis, and only participants who practice breathing at home at least 3 times a week and achieve prescribed breathing rate and ratio for at least 2 time periods after randomization will be included.

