### 3. STUDY DESIGN

We propose a prospective, randomized, double-blinded, study among healthy patients to compare the effects of exhale>inhale versus exhale=inhale on physiological and psychological stress. In a sample of 100 participants we will compare the clinical effectiveness of a 12-week program of slow breathing exercises, consisting of exhale>inhale, to a 12-week program of slow breathing exercises, consisting of exhale=inhale. Outcome assessment will occur at baseline, 6 and 12- weeks for: physiological stress (autonomic tone: heart rate variability, baroreflex sensitivity), and psychological anxiety (PROMIS Anxiety scale, Anxiety Sensitivity Index-3, Beck Anxiety Inventory, Body Vigilance Scale, Panic Disorder Severity Scale, and Perceived Stress Scale-10), affect (PROMIS depression Scale, PANAS-X), and arousal (Epworth Sleepiness Scale, PROMIS Sleep Disturbance Scale]. Psychological measures will be repeated at 26 weeks after study completion as follow-up. **The primary outcomes of the clinical trial will be heart rate variability measured by spectral analysis and psychological stress measured by the PROMIS Anxiety.**

Randomization will occur after baseline testing and assessment of initial compliance to the intervention. Treatment assignments will be generated in a 1:1 ratio stratified by gender. Participants will be randomized to 12 weeks of slow breathing with either exhale>inhale versus exhale=inhale. Each week for 12 weeks, the participant will meet with the mind-body therapist for a 45 minute visit. Participants will be taught the breathing interventions in a private office on the Vanderbilt University campus.

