#### **6.2.5 Completion/Final Evaluation**

- At 12 weeks
  - Autonomic tone
  - Catecholamine Profile
  - Questionnaires: PROMIS Anxiety Scale, Anxiety Sensitivity Index-3 (ASI-3), Beck Anxiety Inventory, Body Vigilance Scale, Panic Disorder Severity Scale, and Perceived Stress Scale-10, PROMIS Depression scale and PANAS-X.
  - Current Medications
  - Concomitant Interventions

Participants who discontinue the study intervention early will require no specific evaluations.

The reason for discontinuation will be documented. If research participants no longer want to participate in the research study, we will terminate them from the study. Participants terminated from the study will undergo no further monitoring or follow-up once they have stopped the study intervention.

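### Section 9.6 plans two between-arm analyses of each primary outcome and does not say which decides; the week-12 contrast from the baseline-adjusted mixed model should be named

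*Combined protocol and SAP*

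**What the plan says.** Section 3 names two primary outcomes: heart rate variability, and "psychological stress measured by the PROMIS Anxiety". Section 9.6 gives both the same treatment.

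- **First analysis.** "The difference between the two treatment groups will be estimated by the mean difference in the within-subject changes, along with their 95% confidence intervals", followed by a t-test. The change runs from baseline to week 12.
- **Second analysis.** "Mixed-effect models will also be used to analyze the data with a random subject effect", with arm, time, arm-by-time and the baseline measurement as fixed effects and change at weeks 6 and 12 as response. In addition: "We will include covariates age, gender, and baseline psychological stress in the models to adjust for their effects".

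The inference sentence that follows calls for an estimate, a 95% interval and a p-value at the 0.05 level, without tying them to either analysis. Roles are assigned elsewhere in the section: multiple imputation is there to corroborate, and the per-protocol analysis is for sensitivity. For missing visits the section turns to the model: "Mixed-effects models are robust in the sense that they can include subjects with missing data at one time point".

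Section 9.3 defines the analysis set: "Our intent-to-treat population will include all participants who are randomized with baseline assessment and at least one post-randomization assessment". Section 6.2.5 adds: "Participants terminated from the study will undergo no further monitoring or follow-up once they have stopped the study intervention".

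**The concern.** Two p-values will exist for each primary outcome, and no rule says which one carries the conclusion. The model has an arm-by-time term, but the section does not say whether the week-12 contrast or an average over visits is intended.

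The two analyses also use different people and different information. A participant with only a week-6 visit belongs to the intention-to-treat set but cannot enter a t-test on 12-week change. Such participants are to be expected, since follow-up ends for those terminated from the study. The t-test uses neither the baseline value nor gender, the stratification factor; the model uses both.

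At stake is mainly precision, if the t-test becomes the main result by default, and an unsettled verdict if the two analyses disagree.

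**Working it through.** **1. The plan's own figure.** Section 9.2 gives an HF HRV difference of 265, SD 406, 38 per arm and two-sided 0.05. A two-sample t-test (noncentral t, 74 df) has noncentrality 265 / (406 × √(2/38)) and power 80.2%. At 280 and 300 it gives 84.3% and 88.9%. These match the stated 80, 84 and 89%, so the sizing is that of the unadjusted t-test. For PROMIS Anxiety (5.2 points, SD 8) the same test gives 79.9% at 38 per arm and 89.6% at the stated 50.

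**2. Effect of baseline adjustment.** Let r be the baseline-to-week-12 correlation and k the week-12 SD divided by the baseline SD. The documents give neither, so both are assumed. With the SD of change held at the planned value,

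adjusted variance / change-score variance = k²(1 − r²) / (1 + k² − 2rk).

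At k = 1 this reduces to (1 + r)/2. One further degree of freedom is lost. For HF HRV at 38 per arm, against 80.2% unadjusted:

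| r | ratio, k = 1 | power | ratio, k = 1.4 | power |
|---|---|---|---|---|
| 0.3 | 0.65 | 93.6% | 0.84 | 86.5% |
| 0.5 | 0.75 | 90.0% | 0.94 | 82.4% |
| 0.7 | 0.85 | 86.1% | 1.00 | 80.2% |
| 0.9 | 0.95 | 82.1% | 0.85 | 86.3% |

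**3. PROMIS Anxiety.** Section 4.1 and Table 1 admit only scores of 45 or more, half an SD below the population mean, and the score is taken with the baseline assessments (Section 4.2). Baseline is therefore truncated from below and week 12 is not, so k = 1 does not fit this outcome. Assume a normal population cut at a = −0.5 SD, with untruncated correlation r:

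- λ = φ(a)/(1 − Φ(a)) = 0.509
- baseline variance v = 1 + aλ − λ² = 0.486 of the population value
- variance ratio = (1 − r²) / [v(1 − r)² + 1 − r²]

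| untruncated r | k | ratio | power, 38 per arm | power, 50 per arm |
|---|---|---|---|---|
| 0.5 | 1.34 | 0.86 | 85.4% | 93.4% |
| 0.7 | 1.24 | 0.92 | 83.0% | 91.8% |
| 0.8 | 1.17 | 0.95 | 81.9% | 91.0% |

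The unadjusted figures are 79.9% and 89.6%, so the gain is about 1 to 6 points.

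**4. How often the analyses disagree.** In simulated complete HF HRV data (38 per arm, bivariate normal, 20,000 runs, the r and k of step 2), the t-test and the baseline-adjusted week-12 test differ on significance in 2–15% of trials at the planned effect. Most of this is the power gain seen again: the t-test alone is significant in only 1–2%.

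**5. Does the planned model hold its level at week 12?** This simulation had 50 per arm, 20% without week 12 (half of them seen at week 6), missing completely at random, and 4,000 runs. The Monte Carlo standard error is √(0.05 × 0.95/4000) = 0.34 points.

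- Random subject effect, common residual variance: null rejection 4.4–5.6% at k = 1, but 6.5–7.0% at k = 1.4. A complete-data check at k = 1.4 gave 6.1–6.8%.
- Unstructured covariance with baseline-by-time (5,000 runs): 4.8–5.5% throughout, with power 84–94% at k = 1 and 82–88% at k = 1.4.

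A completers-only adjusted analysis at 40 per arm gave nearly the same power (84.0–94.7% at k = 1; 82.2–88.1% at k = 1.4). The gain therefore comes from baseline adjustment. Week-6-only members add almost nothing to power; including them keeps the analysis set as defined.

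**The case against.** The strongest reply is that the text already leans to the model. Section 9.6 ties its inference to the effects of interest directly after the mixed-model paragraph, and uses the same phrase when explaining how the model handles missing visits. All analyses are declared intention-to-treat, and the model fits that set better than the t-test does. This stands in part. A reader might infer from the order of the text and from Section 9.2 that the t-test is the primary analysis and that the main conclusion will lose precision. The documents do not support that firmly. They leave the matter open.

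Other points stand as limits:

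- The t-test holds its level, and Section 6.2.3 keeps analysts blinded until the analyses are complete, so neither bias nor steering is at issue.
- A reader might infer an inflated error rate, because either test is significant in about 5.5–7.9% of simulated null trials. That is an error rate only if either result could be claimed, and no section says so.
- Equal-variance formulas suggest PROMIS Anxiety power up to 93% at 38 per arm. The entry criterion makes that too optimistic.
- The calculations assume normal data and equal variances in the two arms, while the pilot change SDs were 248 and 531. Section 9.6 also allows this: "If normality is violated, proper data transformation will be applied or non-parametric analysis methods will be considered". Gains on the raw scale may not carry over.
- A random subject effect is a conventional choice, and the excess rejection appears only if variances differ between visits. The recommended model is thus the planned one with added terms.
- Section 3 names the outcome and does not define the covariate for baseline psychological stress. If that covariate is PROMIS Anxiety, the repeated column in that outcome's model is redundant and leaves the arm estimate unchanged.

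**Conclusion.** The point holds as a gap in pre-specification with a modest gain in precision on offer. It does not show an invalid analysis. Two between-arm analyses of each primary outcome are planned, no sentence ranks them, and no model contrast is named.

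The value of choosing the adjusted analysis rests on an assumed correlation and SD ratio. For HF HRV it runs from nothing (r near 0.7, SD ratio 1.4) to about 14 points of power. For PROMIS Anxiety, under a truncated normal baseline, it is about 1 to 6 points. In none of the cases calculated does adjustment lower power. Naming one deciding analysis is worthwhile whatever the gain, since it settles the verdict when the two disagree. The change should be made because it costs almost nothing and uses data already to be collected.

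**What to change.** State in Section 9.6 that, for each primary outcome, the single deciding analysis is the week-12 arm contrast from the mixed model, with arm, time, arm-by-time, the baseline value of the outcome, gender, age and the planned baseline psychological stress covariate. Label the t-test and multiple imputation as sensitivity analyses.

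Give weeks 6 and 12 their own variances (unstructured 2×2 covariance) and their own baseline slopes (baseline-by-time), because the common-variance random-subject model rejects about 6–7% under the null at week 12 if the week-12 SD is 1.4 times baseline.

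Say which instrument the psychological stress covariate is. If it is PROMIS Anxiety, enter it once in that outcome's model, as a tidy-up.

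The cost is SAP wording and a slightly larger model. No participants, visits or measurements are added, and the sample size in Section 9.2 can stay as it is.
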